### 5.1.3 Experimental Drug Treatment: Drug Therapy

**Prerequisite training for dosing.** A neurosurgeon, neurocritical care physician, or their trained designee will perform hematoma catheter injections under standard sterile technique in the intensive care unit. Viewing a demonstration of the **catheter injection** protocol is mandatory before credentialing a center's physicians and coordinators. A training video has been produced describing the injection procedure and apparatus, sterile field techniques and the exact process for delivering the drug. The training video is available on the trial website ([www.braininjuryoutcomes.com](http://www.braininjuryoutcomes.com)). It will be used continuously to train and retrain personnel administering the injections. A full step-by-step description of drug administration is also available in the MOP. Great care and time has been and will be expended to assure the standardization of safe drug administration. This presentation will be edited as new safety data are developed.

After placement or repositioning of any pre-dosing catheter a six-hour stabilization period is required prior to first dose to assess patient clinical status and minimize rebleeding. During this time, the neurological status of the subject will be assessed to document clinical worsening or improvement. **Surgical Center** confirmation of catheter placement, replacement, or manipulation is also required prior to initiation of dosing. Following surgery, a CT scan is to be obtained and catheter placement approved by the surgical center. This CT scan can be obtained any time prior to administering first dose. Furthermore, a period of at least 6 hours is to be observed prior to first dose to ensure subject is clinically stable.

The pharmacist will prepare the rt-PA and flush as detailed in the Pharmacy Manual, which is part of the MOP. The two prepared syringes containing the rt-PA and flush will be provided by the pharmacy to the appropriate study personnel for administration to the patient. The labels on the syringes must be compared with the patient's records to confirm identity, and to confirm correct dosage, labeling, and correct timing in the series of administration.

**Dosage.** The drug will be administered as a sterile solution and in a sterile manner every 8 ( $\pm$  2) hours for up to 9 doses. The total volume of injectate will equal 1.0 mg rt-PA @ 1 mg/mL plus at least 3 mL of flush or as much flush is needed for the rt-PA to clear the catheter tubing.

**Dosing schedule allowances.** There is a two (2) hour window on either side of the eight (8) hour dosing schedule to allow for scheduling problems, stability determination, INR correction, or any other concern the PI may have regarding giving the dose on schedule. This schedule adjustment should be used as infrequently as possible to maintain a Q8hr schedule for dosing consistency.

**Holding a dose.** If a dose must be held or delayed more than 10 hours to correct an INR value above 1.4 (or other coagulopathy), hold the next scheduled dose, institute corrective therapy and re-assess the INR. Once INR is corrected, dosing may be resumed keeping to the original dose count. If the INR remains > 1.4, continue corrective therapy as required and the investigator may discontinue dosing.

In the event of severe or life-threatening anaphylaxis or hypersensitivity reaction, the treatment phase would be discontinued. The patient would not be retreated with rt-PA. A description of the reaction would be added to the patient's medical record as a serious adverse event for future reference.

**Dosing decision-making by CT.** Before initial dosing and subsequently after every three (3) doses (daily), the investigator is required to view the most recent CT scan to measure clot size and compare to the prior day's scan in order to decide continuation or discontinuation of dosing. As clot size decreases and approaches the target reduction, the next CT may be obtained earlier than after three doses. This process allows the PI and team to confirm that: 1) remaining clot is greater than 10 mL, 2) the blood clot is in direct contact with the catheter, and 3) that the catheter is placed in the clot to be dissolved. Bone windows must be done when obtaining any CT scan in order to confirm that the catheter side ports have contact with the clot. If none of the side ports are in contact with the clot, drug should not be given. Partial contact with the clot should be reviewed by the PI on a daily basis, prior to further dosing.

**Catheter repositioning during dosing.** If these criteria are not met, the catheter must be repositioned. Repositioning to allow for the correct catheter to clot relationship may be performed once under direction of the investigator as needed during the dosing time of the protocol. Open the catheter to drain for 24 hours after the most recent rt-PA administration before repositioning or replacing the catheter. After repositioning obtain a repeat CT scan to confirm catheter placement and clot stability. After both are confirmed and after Surgical Center review, wait six (6) or more hours from the time of catheter repositioning and then resume dosing.

**Stability determination during dosing.** Stability must be demonstrated in the following ways on all CT scans: 1) no expansion of ICH greater than 5 mL as compared to the most previous CT scan, 2) no catheter tract bleed greater than 5mm, and 3) no new IVH or new expansion of IVH. If the clot is stable, dosing may resume.

Repeat CT scans will be performed earlier than every 12 to 24 hours if or when the treating physician determines that there is a sustained improvement or worsening of neurological condition (GCS motor scale score increase or decrease by more than two points for eight hours or more). Therapy will be stopped at this

time if there is any increase in hematoma volume on CT or emergence of systemic bleeding disorders. These additional safety provisions will keep under surveillance the most ideal time to stop rt-PA administration.

Intracranial pressure (if monitored), cerebral perfusion pressure, and blood pressure will be monitored before, during, and after each injection. After injection, the catheter will be closed for 1 hour to prevent drainage of the rt-PA away from the clot and to allow adequate time for drug-clot interaction. After one hour of closure, the catheter will be opened with an appropriate drainage gradient. ICP will be measured every four hours, or more frequently, as clinically indicated. A neurosurgical consult should be obtained for sustained intracranial hypertension. Sustained intracranial hypertension is defined as ICP greater than 20 mmHg for two or more consecutive hours despite maximal medical ICP management.

**Documentation of dosing.** In addition to documenting each dose in the EDC system, each dose administration should be documented in the Medical Administration Record of the medical record as source documentation. A progress note should also be written in the medical record as source documentation to record the date and time of each dose, the amount of rt-PA administered, the amount of flush administered, the catheter in which the drug was administered (when more than one catheter is in place), the time the catheter was closed and reopened, the ICP (if monitored), systolic blood pressure (SBP), and diastolic blood pressure (DBP) prior to the dose and prior to reopening the catheter, and the name and title of the person who administered the dose.

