**Surgical Center review of optimal surgical plan:** The Surgical Center personnel will perform real-time (within six hours of data submission) review of 3D images to instruct the site that the proposed burr hole location and trajectory are appropriate or that a different location/trajectory is recommended. Feedback of the results of their review is documented in the EDC. The site neurosurgeon will proceed with the proposed surgical plan or the Surgical Center recommended plan. If there is disagreement between the two surgical plans, the site neurosurgeon has to demonstrate the rationale of his/her plan before using a surgical plan different from that proposed by the Surgical Center. See the Manual of Operations and Procedures (MOP) for a detailed description of personnel involved, responsibilities, and contact information.

**Catheter placement:** Antibiotic therapy should be administered pre-operatively (hospital protocol or 1-2G Ancef IV; dose is subject-weight dependent) then repeated every eight hours until the catheter is removed (hospital protocol or Ancef IV 1 G Q8hrs). If the subject has a known or suspected penicillin drug allergy, then antibiotic coverage will be administered pre-operatively and continued with each institution's non-penicillin drug of choice until the catheter is removed.

The procedure will be performed in the operating room, procedural CT or MRI scanner, or the ICU. After administration of the appropriate anesthetic, a Mayfield headrest is secured to the subject's head. A reference device is clamped to the Mayfield headrest. The image guidance system unit must be in direct line to the table with no line-of-sight obstruction. Registration is completed by correlating six points on the subject's head to six points on the previously loaded CT scan. Verification of accuracy is accomplished by testing various known landmarks on the subject's face to the image on the computer monitor. Re-registration during the case is accomplished as needed by repeating the correlation of the six landmarks on the subject's head to the CT scan. The procedure is completed in the usual sterile manner for burr hole and catheter placement. Other forms of image guidance which are acceptable include stereotactic robotic arms, electromagnetic tracking without skull fixation (only under general anesthesia and pharmacologic paralysis), or direct "real-time" image guidance in procedural CT or MRI.

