After placement of the catheter and a CT scan to confirm correct placement, a six-hour post-surgical stabilization period is required prior to first injection of rt-PA. Keep the drainage system to drainage for six hours post catheter placement *prior* to first dose of rt-PA. This time is mandated to reduce the possibility of secondary hemorrhage. If new bleeding or bleeding expansion is seen on the post-op CT scan, wait 12 hours and repeat the CT scan. When the bleeding is stable, dosing can be initiated.

If post-operative clot volume is 10 to 15 mL, rt-PA should not be given. The catheter should remain in place and open to drainage for 24-36 hours prior to removal.

**Catheter adjustment/replacement:** Correct catheter placement will be CT-confirmed locally and post-operative measurements will be repeated centrally by the Surgical Center. Catheter adjustments will be made at this time, if necessary. If the hematoma appears larger or the shape is altered on CT scan after the catheter is placed, the catheter may require repositioning and a post-repositioning CT scan to confirm correct placement within the clot as well as stability of clot size. Repositioning is defined as the partial removal or “pull back” of the non-optimally placed catheter. Replacement is defined as removal of the catheter and replacement with a better targeted catheter using the introducer method described above with either the same or a different trajectory of insertion. There is a one-time allowance for a new rigid cannula placement. Soft catheter placements or replacements, usually done through an existing burr hole and always done using a stylet with image guidance, do not count against this limited number of rigid cannula passes. There is no limit to the number of soft catheter placements or replacements as long as stability requirements are met. Occasionally it may be necessary to create a new burr hole/trajectory to access the clot. This will be done only after consultation with the Surgical Center. Repeat CT scan and upload DICOMs of the final catheter placement in the clot into the EDC for Surgical

Center review and approval of catheter location in residual hematoma prior to dosing.

The catheter is then tunneled subcutaneously, connected using sterile technique to a three-way stopcock and then to a closed drainage system. Level the drainage bag to zero.

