If the catheter must be repositioned or replaced after dosing has begun, the procedure must be done equal to or greater than 24 hours after the most recent dose and all stability protocols must be repeated as if this were the original catheter placement.

Complete replacement of the catheter is allowed if the catheter to clot relation has been disturbed by inadvertent catheter movement or partial clot reduction. Complete replacement should be performed only once (i.e., in any subject only two, new rigid cannulas may ever be placed).

If repositioning or replacement does not correct the catheter-clot relation and the rigid cannula has already been replaced once during the trial, rt-PA administration must be stopped or not initiated and the catheter removed 24 hours later. This requirement will control the delivery of rt-PA only into space containing clot that can be lysed. The catheter may be left in place greater than 24 hours later if the catheter supports ventricular drainage as clinically required.

In addition, an unscheduled CT scan must be performed should the subject clinically deteriorate or significantly improve his or her GCS score. These additional safety provisions will keep under surveillance the most ideal time for stopping drug after clot is fully lysed.

**Catheter removal.** After keeping the catheter closed for the one hour following the last dose of rt-PA, the catheter should be opened and then left open to drain for 24-36 hours prior to catheter removal. The catheter must be closed at the time of removal and not open to air to avoid pneumocephalus. The catheter may be left in place greater than 24 hours later if the catheter supports ventricular drainage as clinically required.

To limit infection risk, remove the catheter at the bedside 24 to 36 hours after the last rt-PA administration, unless the catheter supports ventricular drainage as clinically required. Send the catheter tip for culture. A CT scan must be done 24 hours post catheter removal and examined for stability, new bleeding, or hemorrhage extension.

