### 5.3 Concomitant Interventions

- 5.3.1. **Required Interventions.** Intraclot administration of 1mg of rt-PA followed by 3 ml of flush every eight hours for up to nine doses.
- 5.3.2. **Permitted Interventions.** Study center standard of care policies may govern the use of low molecular weight, fractionated and unfractionated heparins for DVT prophylaxis during the acute treatment and follow-up periods. Heparin flushes of systemic lines are also permitted. Use of enoxaparin for DVT prophylaxis in the ICU at the usual doses of 30 mg sc Q12 h or 40 mg sc QD is permitted as long as the patient has good renal function (creatinine clearance of > 30 ml/min) or does not have an unusually low body weight (< 45 kg).

Including but not limited to NovoSeven, fresh frozen plasma, plasma concentrate and vitamin K, are permitted singly or in combination (but not required) for reversal of anticoagulation.

- 5.3.3. **Prohibited Interventions.** During the study period (randomization through the 12 month visit), avoid enoxaparin at therapeutic doses  $\geq 1.0$  mg/kg sc Q12 h.

After the day 30 follow up visit other antithrombotic and antiplatelet agents such as Coumadin (warfarin) and Dabigatran, glycoprotein IIb/IIIa inhibitors (eptifibatide/Integrilin, abciximab/Reopro, tirofiban/Aggrastat), ASA, clopidogrel/Plavix may be administered.

The use of Urokinase, Retevase, Desmoteplase, Tenecteplase or any other thrombolytic agent (other than the study agent) administered via any brain catheter is prohibited. Clogged catheters should be treated with normal saline flushes.

- 5.3.4. **Precautionary Interventions.** If any brain catheter (ICH or IVH, if present) needs to be replaced or repositioned during dosing, wait 24 h after the most recent dose to perform the procedure. A stability CT scan must then be done  $\geq 6$  h after all placements/repositioning to confirm correct placement, clot stability, and absence of significant blood along the catheter tract. Once these are confirmed by the site and Neurosurgical Center, dosing may restart.

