If a subject experiences asymptomatic bleeding (ICH expansion  $< 5$  cc, IVH expansion as assessed by  $< 2$ mm increase in 2 out of 3 ventricular regions, or catheter tract hemorrhage that is  $\leq 5$  mm in the largest diameter), continue the dosing and CT schedule. If the bleeding is larger than these thresholds, with or without mass effect, the next scheduled dose is held and a repeat CT scan is done  $\geq 24$  h after the previous dose. If the ICH, IVH, and catheter tract hemorrhage are stable (i.e., has not further grown by  $> 5$  mm), then dosing may restart.

Particular caution needs to be observed with renal dialysis patients receiving rt-PA. Because this group of patients can experience wide variations in blood pressure with dialysis attendant cardiac volume changes, attention to long-term and intra-procedure blood pressure control is important. Similarly, attention to regional anti-coagulation management is important.

Consider administering platelets to eligible patients who are on antiplatelet therapy (Plavix, aspirin, etc.) at the time of symptom onset. Platelet counts should be closely monitored in this population.

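### After a catheter is moved during dosing, Section 5.1.3 allows rt-PA to restart on an early CT, while Section 5.3.4 requires a CT at least 6 h later

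*Protocol*

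**What the plan says.** The point concerns only a catheter that is repositioned or replaced once dosing is under way. Three parts of the protocol bear on it.

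- **Section 5.1.3, Catheter repositioning during dosing.** The catheter drains for 24 h after the last dose before it is moved. Then: "After repositioning obtain a repeat CT scan to confirm catheter placement and clot stability". Once both are confirmed and the Surgical Center has reviewed, the site is to "wait six (6) or more hours from the time of catheter repositioning and then resume dosing".
- **Section 5.3.4, Precautionary Interventions.** For any brain catheter moved during dosing there is the same 24 h interval after the last dose. The stability CT must be done at least 6 "h after all placements/repositioning to confirm correct placement, clot stability, and absence of significant blood along the catheter tract". Dosing may restart only when the site and the neurosurgical center have confirmed these on that scan.
- **Section 5.1.2, Catheter adjustment/replacement.** After dosing has begun, "all stability protocols must be repeated as if this were the original catheter placement". For an original placement, Section 5.1.2 puts the CT ahead of the wait ("After placement of the catheter and a CT scan to confirm correct placement, a six-hour post-surgical stabilization period is required"), and Section 5.1.3 says of the post-surgical scan: "This CT scan can be obtained any time prior to administering first dose".

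Section 5.3.4 also states what the scan is meant to catch. Small asymptomatic bleeds let dosing continue, but "If the bleeding is larger than these thresholds, with or without mass effect, the next scheduled dose is held".

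**The concern.** Two sections govern one event and differ on when the CT that clears the dose may be taken. The six-hour wait after a catheter is placed exists to lower the risk of secondary bleeding (Section 5.1.2). Section 5.1.3 keeps the wait but does not require a scan at the end of it, so a bleed that develops during the wait need not be looked for. What is at stake is a thrombolytic dose into a recently manipulated hematoma when the protocol's own rule would have held that dose.

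**Working it through.** No sample size, power or alpha figure is involved. The check sets the two rules side by side and adds up the stated intervals.

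**Inputs**
- Interval from last dose to manipulation: 24 h (Sections 5.1.2, 5.1.3 and 5.3.4).
- Minimum wait from manipulation to next dose: 6 h (Section 5.1.3).
- Minimum interval from manipulation to clearing CT: none stated (Section 5.1.3); 6 h (Section 5.3.4).
- Dosing interval: 8 h (Section 5.1.3, Dosage).
- Routine CT: at least daily and at least after every three doses (Sections 5.1.3 and 6.3.9).
- Surgical Center review time: not stated for this scan. I assume 0 to 6 h, borrowing the turnaround given for surgical plans in Section 5.1.2: "The Surgical Center personnel will perform real-time (within six hours of data submission) review of 3D images".

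**Timeline, in hours from the last rt-PA dose**

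| Step | Section 5.1.3 | Section 5.3.4 |
|---|---|---|
| Earliest manipulation | 24 | 24 |
| Earliest clearing CT | 24 | 24 + 6 = 30 |
| Central review (assumed 0 to 6 h) | runs during the wait | 30 to 36 |
| Earliest restart dose | 24 + 6 = 30 | 30 to 36 |

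Under Section 5.1.3 the gap between the clearing scan and rt-PA can be 30 − 24 = 6 h, or longer if the dose is given later. Under Section 5.3.4 it is only the review time.

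**Can both rules be met?** Yes. A CT at 6 h or later satisfies every section. A CT before 6 h satisfies Section 5.1.3, and Section 5.1.2 as read above, but breaches Section 5.3.4. This is a laxer rule against a stricter one, and no text says which controls.

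**What happens to a silent bleed that develops during the wait?**
1. It exceeds a Section 5.3.4 threshold (ICH growth under 5 cc, ventricular growth under 2 mm in two of three regions, or tract blood up to 5 mm would let dosing continue), so the next dose should be held.
2. The early scan predates it, and Section 5.1.3 asks for no other scan before the restart dose.
3. The unscheduled CT in Section 5.1.2 depends on clinical change, so it is not triggered.
4. Routine imaging limits exposure but need not precede the restart dose. With a restart at 30 h, doses at 30, 38 and 46 h could all be given before the three-dose rule forces a scan.

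**Frequency.** The documents do not give the number of subjects whose catheter is moved during dosing. Appendix 8 expects rebleeding with neurologic deterioration in 3.6%, radiographic rebleeding into the surgical bed in 15% and catheter-tract bleeding in 30%. These figures are not specific to repositioning or to bleeds above the thresholds, so they give no event rate here. They do show that bleeding seen on imaging is expected more often than bleeding with deterioration.

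**The case against.** The strongest reply is that Section 5.1.3 is silent on CT timing rather than permissive. Read as one document, the mandatory and more specific rule in Section 5.3.4 fills the silence, the hazard arises only if a site departs from it, and what is missing is a cross-reference. It is true that both rules can be met together. But Section 5.1.3 is the dosing section, it has a paragraph on exactly this event, and it puts confirmation and review ahead of the wait. That order points to an early scan.

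Second, the sentence allowing the CT at any time concerns the first dose after surgery and may be only a position check. Section 5.1.2 carries over stability requirements without naming that sentence. This is a fair limit on the support from Section 5.1.2. The conflict between Sections 5.1.3 and 5.3.4 does not depend on it.

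Third, the Surgical Center stands between manipulation and dose under both rules. Under Section 5.1.3, however, the scan it reviews may be the early one. The statement in Section 10.3.3 that the surgical teams advise on dosing describes review just before randomization.

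Fourth, the daily and every-three-doses CT caps exposure, and blood pressure and cerebral perfusion pressure (with ICP where monitored) are checked around each injection. This stands as a limit on harm. It does not require a scan before the restart dose.

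Finally, the harm needs several things to coincide, its frequency is unknown, and the Manual of Operations, which holds the step-by-step dosing instructions, may settle the matter. All of this is correct. It bears on how serious the point is, not on whether the protocol text conflicts.

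**Conclusion.** The concern holds. For a catheter repositioned or replaced during dosing, Section 5.1.3 can be followed to the letter with a clearing CT from 24 h after the last dose and rt-PA at 30 h, whereas Section 5.3.4 requires that CT at 30 h or later. A site following Section 5.1.3 can give rt-PA over a silent, above-threshold bleed that arose after its scan, and up to three doses could precede the next required CT. The first dose after surgery has its own rule and is not in conflict.

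The number of subjects affected and any effect on the reported bleeding rate cannot be quantified from the documents. The conclusion rests on the protocol text alone; the Manual of Operations was not available. This is a safety wording conflict that should be fixed. It does not alter the efficacy design.

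**What to change.** Make the Section 5.3.4 rule the only restart rule.

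- **Section 5.1.3, Catheter repositioning during dosing.** Replace the restart instruction with wording such as: *The CT that clears the next dose is taken no sooner than 6 hours after the catheter was repositioned or replaced. rt-PA restarts only when the site and the Surgical Center have both confirmed, on that scan, catheter position, a stable clot and no significant blood in the catheter tract. A scan taken sooner may be used to check position but does not clear the dose.*
- **Section 5.1.2, Catheter adjustment/replacement.** Add that, once dosing has begun, this rule applies in place of the first-dose CT timing.
- **Optional.** Add a check in the EDC that the clearing CT is timed at least 6 h after the recorded catheter manipulation.

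**Cost.** Two wording changes and, if wanted, one EDC check; Section 5.3.4 already mandates the scan. Sites that now scan early could no longer have the review done during the wait. With review taking 0 to 6 h, as assumed above, the restart moves from 30 h to between 30 and 36 h, a delay shorter than one 8 h dosing interval. A misplaced catheter may be found later unless the site also takes an early position scan.

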We consider both bacterial ventriculitis and bacterial meningitis compulsory SAEs and treat both the same. This is the most conservative safety profile. We provide separate SAE codes for a clinical determination between ventriculitis and meningitis and bacterial and non-bacterial, to accommodate investigator diagnostic classifications.

**Procedures for modification.** Injections of rt-PA will be discontinued for all symptomatic hemorrhage occurrences. No other modification of “best care” is anticipated for symptomatic hemorrhage. All care associated with this event will be recorded on the SAE eCRF. Injection of rt-PA will not be discontinued for infection. The same adverse event reporting will be employed.

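### Protocol 5.1.3 and 5.3.4 give opposite rt-PA dosing instructions for a small asymptomatic IVH expansion

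*Protocol*

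**What the plan says.** Protocol section 5.1.3, under the paragraph on stability determination during dosing, states: "Stability must be demonstrated in the following ways on all CT scans". Three criteria follow: ICH growth of no more than 5 mL since the previous scan, a catheter tract bleed of no more than 5 mm, and "no new IVH or new expansion of IVH". The paragraph ends: "If the clot is stable, dosing may resume". The first two criteria carry a numeric tolerance; the IVH criterion carries none.

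Protocol section 5.3.4 (Precautionary Interventions, within 5.3) deals with asymptomatic bleeding. It lists ICH expansion below 5 cc, IVH expansion of less than a 2 mm "increase in 2 out of 3 ventricular regions", and a catheter tract hemorrhage of at most 5 mm. For these the site is to "continue the dosing and CT schedule". Above them: "If the bleeding is larger than these thresholds, with or without mass effect, the next scheduled dose is held", with a repeat CT at least 24 hours after the previous dose. Dosing may restart if ICH, IVH and tract are stable, which is explained in parentheses as meaning that the bleeding "has not further grown by" more than 5 mm.

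Section 7 adds: "Injections of rt-PA will be discontinued for all symptomatic hemorrhage occurrences".

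**The concern.** The two sections speak to the same decision: whether the next rt-PA dose is given after a routine scan that shows slightly more ventricular blood in a patient without symptoms. One makes the absence of any IVH expansion a condition for dosing; the other instructs the site to carry on.

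The drug is a thrombolytic given through a catheter into the hematoma, so the limit at which growing ventricular blood halts dosing is a safety threshold. The synopsis plans about 90 to 100 centers, and with two rules in the text they can act differently on the same finding. Asymptomatic intracranial bleeding is one of the monitored safety measures (section 9.1). Deviations in drug administration are reviewed (section 9.2), and protocol deviations must be reported within 24 hours (section 10.3.10), so a site that follows 5.3.4 could be cited for breaching 5.1.3.

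**Working it through.** No sample size, power or error rate is involved, so the check is a comparison of the two rules.

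**Step 1: is it the same decision point?** Section 5.1.3 requires the investigator to review a CT before the first dose and after every three doses in order to decide whether dosing continues. Section 6.3.9 says the daily scan monitors for asymptomatic bleeding, among other things, and is evaluated before the next rt-PA administration. The routine dosing scan therefore triggers both rules.

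**Step 2: limits side by side, asymptomatic patient.**

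| Finding | 5.1.3: stable if | 5.3.4: continue if | Agreement |
|---|---|---|---|
| ICH growth | not above 5 mL | below 5 cc | Yes, except at exactly 5 mL |
| Catheter tract bleed | not above 5 mm | at most 5 mm | Yes |
| IVH expansion | none | below 2 mm in 2 of 3 regions | No |
| New IVH | none | not covered; the allowance names expansion only | No conflict |

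**Step 3: test case.** Take, as an illustration, an asymptomatic patient whose daily CT shows a 1 mm IVH increase in 2 of 3 ventricular regions.

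- Under 5.1.3, the third criterion fails, the patient is not stable, and the condition for dosing is not met.
- Under 5.3.4, 1 mm is below 2 mm, so dosing continues without a hold.

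For an expansion larger than the 5.3.4 threshold, both sections point away from giving the next dose. The conflict therefore occupies the range above zero and below 2 mm in 2 of 3 regions.

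**Step 4: the restart wording in 5.3.4.** This applies to a later decision, on the repeat CT after a hold. The 5 mm figure follows a list of ICH, IVH and tract, but its unit fits only the tract: ICH is measured in mL or cc, and IVH was given its own 2 mm rule one sentence before. Read literally for IVH, a dose held for exceeding the 2 mm limit could restart after further growth of up to 5 mm, which 5.1.3 does not allow. This is a separate drafting defect and does not add another limit to the decision in step 3.

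**Step 5: frequency.** The nearest figure is in Appendix 5, where enlargement of ventricular system hemorrhage makes up 1.75% of 573 MISTIE II events: 0.0175 × 573 = 10.03, about 10 events (10/573 = 1.745%). These are not split by size, symptoms, arm or dosing period. They show that IVH enlargement occurs, but they give no rate for small asymptomatic expansion during dosing.

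**The case against.** The best defence is that the sections can be harmonised. On this reading 5.1.3 is a short checklist and 5.3.4 is the operational rule: it says how IVH expansion is assessed and when to continue, hold or rescan. For ICH and tract its limits match the checklist in size, which suggests that it also supplies the IVH measure that 5.1.3 leaves unquantified. In addition, 5.1.3 never says in so many words to hold a dose. Its only stated action is that dosing may resume, and it directly follows a paragraph on catheter repositioning, so it might govern resumption only.

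Part of this stands. The harmonised reading is plausible and may be what was meant, and a hold under 5.1.3 follows by implication from a mandatory condition. But the reading is not written down. Two criteria with numeric limits followed by an unqualified one will reasonably be taken as zero tolerance for the third, and neither section points to the other. The resume-only reading does not survive the paragraph's heading, which refers to the dosing period, or its application to all scans. Repositioning already has its own paragraph with its own resume rule.

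It is also fair to point to existing controls:

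- Symptomatic hemorrhage ends dosing (section 7).
- The Surgical Center guides dosing decisions (section 10.3.3).
- Uploaded scans are reviewed for stability and to support dosing decisions (section 10.3.9).
- Asymptomatic cerebral bleeds are medical events of interest and receive the same review as serious adverse events (section 10.4.1).
- The Manual of Operations describes drug administration step by step (section 5.1.3).

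These limit the consequences. None of the protocol provisions says which rule decides the next dose. The manual was not available for this review and may do so, but the protocol itself would still contradict itself.

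**Conclusion.** The concern holds. As written, sections 5.1.3 and 5.3.4 give opposite answers for an asymptomatic IVH expansion below 2 mm in 2 of 3 ventricular regions, and the protocol does not say which governs. The conclusion rests on reading the stability requirement in 5.1.3 as a condition for the next dose, which its heading and its application to all scans support.

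The scope is narrow: small, asymptomatic expansion in surgical patients during dosing. No number of affected patients can be given, and there is no effect on endpoints, power or analysis. It should still be corrected, because it concerns the threshold for continuing an intracranial thrombolytic and the correction is cheap.

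**What to change.** Use one IVH rule in both sections; the clinical leadership chooses the limit.

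- If small expansion is to be tolerated, reword the third criterion in 5.1.3 so that it excludes new IVH and any IVH expansion at or above the 5.3.4 threshold.
- If zero tolerance is intended, delete the IVH allowance from 5.3.4 so that any IVH expansion holds the next dose.

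In either case, replace the single 5 mm restart figure in 5.3.4 with separate limits: ICH in mL, IVH at the chosen hold limit, and catheter tract at 5 mm. Add a cross-reference between the two sections.

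The cost is a clarification of two protocol sections and a notice to sites. Nothing changes in the endpoints, analysis or sample size.
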